10.2 Statistical Analysis

Statistical analysis and report writing will be performed by the sponsor. De-identified data will be provided to the sponsor by each site for the sponsor to perform the analyses. Each site will only have access to the data collected at their site.

Statistical analyses will be conducted on all randomized subjects who have successfully completed the study without a protocol deviation that may be regarded as impacting the assessments of primary hypothesis. The overall type I error rate will set at $\alpha=5\%$ level. All primary hypotheses must be met in order to satisfy the objective of the study.

Descriptive statistics will be generated at baseline/dispense and each follow up visits (e.g. mean, SD). In each case, Noninferiority will be concluded if the low limit of 95% confidence interval of difference in subjective response is above the low bound: -10. Paired testing, ANOVA, or mixed linear model may also be used for additional analysis on selected variables. Binomial test was used to analysis the results for the count data of subjective preferences; the number of "no preference" were evenly distributed to the two options on the basis they would be equally likely to choose either. A p-value less than or equal to 0.050 will be regarded as statistically significant.

11 Data Quality Assurance

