CooperVision™

PROTOCOL

**DAILY DISPOSABLE DISPENSING CLINICAL TRIAL OF NEPTUNE LENS
AGAINST MYDAY LENS**

Sponsor Study Code: CV-16-60
Version Number: 2.3
Implementation document Date: 31 AUG 2016
Sponsor Company: CooperVision, Inc.
Study Category: Design Validation
Clinical Sites: CORL, Indiana University
TOSI, University of Houston

Protocol Sponsor:

[Redacted]

Date

[Redacted]

[Redacted]

Site Principal Investigator:

[Redacted]

Date:

[Redacted]

[Redacted]

Site Principal Investigator:

[Redacted]

Date:

[Redacted]

TABLE OF CONTENTS

1	Introduction	5
2	Study Objective	5
2.1	Study Hypothesis	5
3	Study Design	5
4	Ethics Review / Statement of Compliance	6
4.1	Relevant Standards / Guidelines	6
4.2	Institutional Review Board	6
4.3	Informed Consent	7
5	Clinical Trial Registration	7
6	Potential Risks and Benefits to Human Subjects	7
7	Materials and Methods	8
7.1	Subjects.....	8
7.2	Number of Sites.....	9
7.3	Study Materials.....	9
7.4	Visit Schedule and Procedures.....	12
8	Adverse Event Reporting	20
8.1	Adverse Event Definitions.....	20
8.2	Procedures for Adverse Events	22
8.3	Reporting Adverse Events	23
8.4	Discontinuation from the Study	23
9	Device Malfunctions	24
10	Statistical Analysis	24
10.1	Sample Size Calculation.....	24
10.2	Statistical Analysis	25
11	Data Quality Assurance	25
11.1	Study monitoring.....	25
11.2	Sponsor Responsibilities	26
11.3	Investigator Responsibilities	26
11.4	Record keeping	27
11.5	Record retention	27
12	Protocol Deviations	28
12.1	Major protocol deviations.....	28
12.2	Minor protocol deviations.....	28
13	Data Entry / Data Management	29
13.1	Confidentiality	29

13.2Publication.....	29
14 Study Costs	29
15 Study Report	29
16 Appendix	30
16.1Appendix 1	30
16.2Appendix 2	31
16.3Appendix 3	33

1 Introduction

CooperVision is evaluating the clinical performance of MyDay 1-Day lenses (Neptune test lenses)

[REDACTED]

2 Study Objective

The purpose of this study is to investigate the overall clinical performance of the Neptune daily disposable silicone hydrogel lens (test) compared to the MyDay lens (control).

This is a study to validate the performance of Neptune lenses when worn on a daily disposable wear modality over 1 month (for each lens).

The primary variables of interest are:

- Comfort (subjective ratings)
- Vision (logMAR, high and low illumination, and subjective ratings)
- Anterior ocular health (corneal staining, conjunctival staining and hyperemia)

Secondary variables are:

- Lens fit performance

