10.1 Sample Size Calculation

A sample size of 60 completing subjects is sufficient to detect a mean difference of 10 (0 – 100) in subjective ratings and 30% difference in ocular health incidents assuming $\alpha=0.05$ and a power of 80% (Table 3). Approximately 70 subjects will be enrolled assuming the dropout rate of 10% to 15%. This calculation is based on two sites completing a specific number of subjects to give a total of 60 completed subjects.

Table 3: Sample Size Calculations

	Subjective responses	Ocular Health
Difference between pairs	10	-
SD between pairs	15	-
Comparison Proportion (p1)	-	40%
Baseline Proportion (p2)	-	10%
Sample size of completion	60	
Type I (α)	5%	
Power (1- β)	80%	

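### Splitting no-preference answers evenly before the binomial test overstates its variance and costs power to detect a preference for either lens (minor, supportive analysis)

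*Combined protocol and SAP*

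**What the plan says.** Section 10.2 of the combined protocol and SAP states: "Binomial test was used to analysis the results for the count data of subjective preferences". The answers expressing no preference "were evenly distributed to the two options on the basis they would be equally likely to choose either". The decision rule is general: "A p-value less than or equal to 0.050 will be regarded as statistically significant".

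The section does not state whether the test is one- or two-sided, what share of subjects is expected to express no preference, how an odd number of such answers is divided, or whether an analysis without them will be shown.

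Section 2 lists comfort, vision and anterior ocular health as the primary variables. Preference is not among them, although some secondary entries are redacted. The main decision on subjective ratings is separate: "Noninferiority will be concluded if the low limit of 95% confidence interval of difference in subjective response is above the low bound: -10".

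**The concern.** A binomial test on N responses treats each response as an independent 50:50 choice under the null. Subjects with no preference made no choice. Giving exactly half of them to each lens adds the same fixed number to both counts, so those responses contribute nothing to the random variation that the test assumes they have.

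The plan's reason for the split, that these subjects would pick either lens with equal probability, describes random allocation. That would generate the binomial variance. A fixed even split does not, so the reason does not support the rule.

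The consequence is a test with too little power, in both directions. A real preference for the control lens is as likely to be missed as one for the test lens. In a design validation study, overlooking the former is not a safe error.

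**Working it through.** **Inputs from the documents.** N = 60 completers (section 10.1); significance at p ≤ 0.050 and the even split (section 10.2).

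**Assumptions, because the plan gives no figure.** Two-sided exact binomial test; share of ties q from 0 to one half; a true preference of 70:30 among choosers, with 65:35 to 80:20 as the range. When T is odd, one tie is dropped so that the split is even.

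**The plan's own figure.** Section 10.1 claims no power for preference, so there is none to reproduce. The 60 comes from other endpoints. The unpooled two-proportion formula for 40% against 10% gives (1.96 + 0.842)² × (0.4×0.6 + 0.1×0.9) / 0.3² = 28.8, or 29 per group and 58 in all. The paired formula for ratings needs (15 × 2.802 / 10)² = 17.7, or 18. I use 60 only as N.

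**Step 1: variance.** Let X be the number preferring the test lens among the N-T choosers. The planned test uses X + T/2 out of N.

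- Actual null variance: Var(X + T/2) = Var(X) = (N-T)/4.
- Variance the test assumes: N/4.
- Overstatement: N/(N-T), which is 60/48 = 1.25 at T = 12, 60/40 = 1.50 at T = 20 and 60/30 = 2.00 at T = 30. At T = 20 the variances are 15 assumed and 10 actual.

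**Step 2: type I error and power.** Exact enumeration with T ~ Binomial(60, q):

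| Tie rate q | Size: split | Size: excluded | Power at 70:30: split | Power at 70:30: excluded |
|---|---|---|---|---|
| 0 | 2.7% | 2.7% | 84% | 84% |
| 5% | 2.8% | 3.9% | 82% | 85% |
| 10% | 2.4% | 3.7% | 78% | 82% |
| 20% | 1.7% | 3.7% | 67% | 77% |
| one third | 0.9% | 3.5% | 47% | 68% |
| one half | 0.2% | 3.1% | 20% | 52% |

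**Step 3: other preference strengths.** Power with T fixed, split against excluded:

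| True preference | T = 12 | T = 20 | T = 30 |
|---|---|---|---|
| 65:35 | 35% vs 47% | 21% vs 44% | 6% vs 36% |
| 70:30 | 64% vs 75% | 44% vs 70% | 16% vs 59% |
| 75:25 | 88% vs 93% | 72% vs 90% | 35% vs 80% |
| 80:20 | 98% vs 99% | 91% vs 98% | 61% vs 94% |

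**Step 4: smallest significant result.** For an even T, the split test always needs 39 against 21, a lead of 18. Among choosers alone:

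| T | Choosers only | Split rule needs, among choosers |
|---|---|---|
| 6 | 35-19 (lead 16) | 36-18 |
| 12 | 32-16 (lead 16) | 33-15 |
| 20 | 27-13 (lead 14) | 29-11 |
| 30 | 21-9 (lead 12) | 24-6 |

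**Step 5: example.** Take 27 against 13 with 20 ties. Among choosers, 27 of 40 gives p = 0.038. After the split, 37 of 60 gives p = 0.092. The difference over all respondents is the same either way: (27-13)/60 = (37-23)/60 = 0.233. Its standard error, keeping the ties as zeros, is √[(40/60 - 0.233²)/60] = 0.101. The Wald 95% CI is therefore 0.035 to 0.431, which excludes zero.

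**Step 6: can the split ever help?** At N = 60, no outcome is significant after splitting but not after excluding ties. The rule can only lose detections.

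**The case against.** The strongest defence is that the rule is disclosed, keeps every respondent in the test, and cannot produce a false claim: size stays below 5% and the estimated difference is untouched. A test among choosers can be significant on a small choosing minority, so some statisticians would keep the ties and accept the conservatism. The stated reason could also be read as random allocation, for which N/4 is the right variance.

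The magnitude is assumed throughout. At 80:20 the loss is small unless ties are common, and the largest losses need about half the subjects to express no preference. At low tie rates part of the gap is discreteness of the exact test: power with 5% ties excluded (85.0%) slightly exceeds power with no ties at all (83.8%), because the cut-off at n = 60 happens to be strict (size 2.7%). The 27-13 example is the smallest significant result at 20 ties, and its interval is not independent confirmation, since it too gives ties no weight in the lead.

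These points limit the size of the finding but leave the mechanism intact. The text specifies an even distribution, which is fixed. Random allocation would restore the variance only by adding noise to the result. The worry about a small choosing minority is met by reporting the no-preference count and an interval over all respondents, which use everyone with the correct variance.

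**Conclusion.** The concern holds, as a minor one. The fixed even split overstates the null variance by N/(N-T), makes the p-values too large, and lowers power equally for a preference towards either lens. Under the stated assumptions at 70:30, the loss is about 3 points at 5% ties, 5 at 10%, 11 at 20%, 21 at one third and 33 at one half. Part of the gap at 5% and 10% is exact-test discreteness. With no ties there is no loss.

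The mechanism and direction rest only on the plan's wording. The size rests on a tie rate, preference share and sidedness that the documents do not give. Type I error remains controlled, the estimated difference is unchanged, and the -10 non-inferiority rule for ratings is unaffected. Preference is not a visible primary variable; because some secondary entries are redacted, its exact rank cannot be confirmed.

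**What to change.** In section 10.2, delete the even-split rule and state instead:

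> Preference will be tested with an exact two-sided binomial (sign) test among subjects stating a preference; the number and percentage with no preference will be reported, with a 95% CI for (test preferred minus control preferred) over all respondents.

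This also settles the sidedness of the test and removes the question of how to divide an odd number of ties. It costs one sentence and needs no extra data or subjects.

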11.1 Study monitoring

Site qualification of the investigative site has been completed to ensure that the site facility is adequate, personnel are qualified and resources are satisfactory to conduct clinical studies for the Sponsor. The protocol will be reviewed by the investigators prior to enrollment of the first subject. This will involve an overview of the protocol, which includes information on study objectives, inclusion and exclusion criteria, study visits and adverse event reporting. Data

collection forms will also be reviewed and this will provide an opportunity to discuss any questions.

Central study monitoring will involve regular study updates from the clinical site to the sponsor. The updates will include the number of subjects enrolled, the number eligible, the number completed and whether there have been any unscheduled visits, discontinuations, significant or serious adverse events or major protocol deviations. These updates will be provided weekly.

A site visit may be conducted during the course of the study as appropriate. Prior to final data freeze, a close-out visit/discussion may be warranted to check for accuracy and completeness of records. The sponsor or sponsor's representatives will be authorized to gain access to the source documentation for the purposes of monitoring and auditing the study.

11.2 Sponsor Responsibilities

The Sponsor is responsible for the selection of the Investigator and study site, and should also select and appoint a monitor. The Sponsor has the ultimate responsibility for monitoring. The Sponsor is to supply and keep an up-to-date signed protocol and protocol amendments, and provide devices which are the Subject of the clinical investigation.

The sponsor should ensure: appropriate information is provided to the Investigators to conduct the clinical trial; that deviations are reviewed with the Investigator as needed and included in the final report. Adverse events are reported by the Investigator, and the sponsor in turn will then notify their applicable regulatory authorities, and other investigators as appropriate. The Sponsor is to maintain Sponsor-specific clinical trial documentation as required by the regulatory authorities and to ensure the Investigator is aware of their record keeping responsibilities.

11.3 Investigator Responsibilities

The Investigator is responsible for ensuring subject safety and data quality by: protocol compliance, adherence to GCP and local regulatory requirements, and the Declaration of Helsinki. The Investigator should be appropriately qualified and legally entitled to practice, and be trained in the proper method of obtaining informed consent.

The Investigator must have the appropriate resources to conduct the clinical trial, be familiar with the protocol and agree to adhere to it, support monitoring and auditing activities, communicate with the Sponsor regarding any clinical trial issues or need for protocol modifications, make the necessary arrangements to ensure proper conduct and completion of the clinical trial, and ensure the protection and welfare of the subject, including arranging any emergency treatment as needed.

The Investigator must ensure written IRB approval is received prior to the start of the clinical trial, that the IRB and Sponsor is kept informed of the clinical trial progress, including serious/adverse

events and deviations as required by them, and that any changes to the protocol are notified to the IRB and review written approval prior to implementation.

The Investigator must try to ensure adequate subject recruitment; that all necessary and appropriate information is given to potential subjects to ensure informed consent; is taken and documents; and that clinical records indicate the subject is enrolled in a clinical trial. The Investigator must ensure that clinical trial subjects are provided with emergency contact details along with a procedure to follow in the case of an emergency, and that clinical trial subjects are kept informed as pertinent new information becomes available that may affect their decision to participate.

The Investigator has primary responsibility for the accuracy, legibility and security of all clinical investigation data, documents and subject records at the Investigator site during and after the clinical trial. CRFs are to be signed by the Investigator, and any alterations to data are to be by authorized personnel, initialed and dated by same or, in the instance of electronic data, an audit trail must be in place, with no obstruction of the original data.

The Investigator must ensure that data be kept for the minimum time as specified by this protocol, ~~test product must be accounted for (the quantity of the devices received must be reconciled with the quantities of the device used, discarded or returned),~~ and must also be responsible for the supervision and assignment of duties to all responsible for the conduct and evaluation of the clinical trial for the Investigator center involved.

11.4 Record keeping

Detailed records of all study visits will be made using the Case Report Forms (CRFs). All data recorded on forms will be in ink. Any corrections to the forms will be initialed and dated at the time they are modified.

Study subject records will be completed to comply with GCP guidelines. Records will contain:

- Unique study acronym and/or code;
- Subject ID;
- Date enrolled;
- Confirmation by investigator that subject met eligibility criteria;
- Confirmation that subject received a signed and dated copy of informed consent;
- Exit date;
- Investigators signature confirming study exit.

11.5 Record retention

Following study completion, data will be available in electronic and/or paper format for audit, sponsor use, or subsequent analysis. The original clinical raw data (including completed CRFs

and Informed Consent forms) will be retained according to investigative site guidelines, but as a minimum for 3 years. The Sponsor will be notified and consulted if ever the files are to be destroyed. In the event that this protocol is indicated for design verification and validation purposes, as indicated on the title page, copies of all original raw data forms and copies of completed CRF's (with personal identifiers removed) can be forwarded to the sponsor after completion of the final report, at the sponsor's request.

12 Protocol Deviations

Protocol deviations are unanticipated or unintentional changes to a study after it has received prior sponsor approval and ethics clearance. Protocol deviations can be major or minor.

12.1 Major protocol deviations

Major protocol deviations may impact the research protocol, information consent document or other study materials, usually cannot be anticipated ahead of time and are often necessary to ensure the safety and welfare of the subjects.

The following are examples of protocol deviations that must be reported to the ORE/IRB:

- Changes in procedures initiated to eliminate immediate risks/hazards to subjects;
- Enrollment of subjects outside the protocol inclusion/exclusion criteria whether agreed to or not by the sponsor;
- Medication / device / intervention errors (i.e. incorrect drug or dosage of drug / incorrect contact lens(es) dispensed / incorrect care system dispensed);
- Inadvertent deviation in specific research intervention procedures or timing of the research intervention which could impact upon the safety or efficacy of the study-related intervention or upon the experimental design;
- Information consent documentation violations: no documentation of informed consent; incorrect version of, or incomplete, informed consent documentation used.

12.2 Minor protocol deviations

Protocol deviations caused by or which originate with research subjects are considered minor, and normally are not reported to the ORE/IRB unless these result in increased risk to the subject(s). The following are examples of protocol deviations that are considered minor and do not require reporting to the ORE/IRB:

- Logistical or administrative aspects of the study (e.g., study subject missed appointment, change in appointment date);
- Inadvertent deviation in specific research intervention procedures or timing of the research intervention which would not impact upon the safety or efficacy of the study-related intervention or upon the experimental design (i.e., missing a measurement during a session that is not considered critical for the study).

12.2.1 Reporting and documenting protocol deviations

Major protocol deviations must be reported to the ORE/IRB according to its guidelines.

All protocol deviations (major and minor) occurring during the study will be documented and included in the final report.

[figure not shown]
13 Data Entry / Data Management

Data will be entered into an electronic spreadsheet. Study staff will only be able to modify the data file via password entry. The investigators will be responsible for the data integrity, and complete data entry for each visit as well as the take home questionnaires. The investigator will send the data collected to the study sponsor within approximately 5 business days after the last subject completes the final visit. In addition, a full one month dataset will be provided to the sponsor at the sponsor's request. Investigators will be masked for the interim analysis.

